8.1 Imorphics MRI Assessments

The analyses of the imorphics MRI will be made on the ITT group and on the PPS population.

The observed values and the derived change from baseline values will be listed and summarized descriptively for the following MRI variables:

- MRI of the bone area of the medial femur for the target knee.
- MRI of the cartilage thickness for the target knee.
 - CM_FEMUR_THCTAB: Average thickness of cartilage in the central medial femur region
 - CM_TIBIA_THCTAB: Average thickness of cartilage in the central medial tibia region
- MRI of the total bone marrow lesion volume for the target knee

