#### 3.2 Secondary Objectives Study Population A

To assess, in patients with symptomatic and radiographic knee OA, over 52 (26+26) weeks:

- The effect of MIV-711 on MRI cartilage thickness loss
- The effect of MIV-711 on MRI bone marrow lesion volume
- The effect of MIV-711 in the semi quantitative MRI Osteoarthritis Knee Score (MOAKS) parameters
- To assess the effect of MIV-711 on MRI knee joint bone area.

Note: all MRI assessments refer to the target knee unless stated otherwise.

Target knee is identified by knee pain on a numeric rating scale and Kellgren and Lawrence classification grade. If patients have knee pain in both sides with equal regard to these two criteria, the right knee should always be prioritized. The target knee in Study MIV-711-202 must be the same as in Study MIV-711-201.

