### 7.2 Secondary Endpoints (Study Population A)

Bone parameters will be measured from MRIs of the bone area taken at Visit 2 (Enrolment) and Visit 8 of Study MIV-711-201 as well as the MRI of the bone area taken at Visit 5 in Study MIV-711-202.

MRIs will be analysed semi-quantitatively by a central experienced musculoskeletal radiologist using the MOAKS [36] and quantitatively using statistical shape modelling (SSM, Imorphics Ltd) for the features below. [23, 37, 38]

MOAKS scoring will be used to assess the following features:

- Bone marrow lesions (BMLs) and cysts: 15 sub-regions graded for BML (including ill-defined lesions and cysts) size in regard to the total volume of the sub-region occupied by BML(s). Grade 0=none, grade 1<33% of sub-regional volume, grade 2=33–66% of sub-regional volume and grade 3>66% of sub-regional volume.
- Articular cartilage: 14 articular cartilage regions graded for size of any cartilage loss (including partial and full thickness loss) as a % of surface area as related to the size of each individual region surface and % of loss in this sub-region that is full-thickness loss.
- Osteophytes: 12 sites scored for presence and size of osteophytes. Grade 0=none; Grade 1=small; Grade 2= medium; Grade 3= large.

Bone shape modelling of MRI will be used to assess:

- Mean cartilage thickness (mm) for each of the anterior, posterior and central regions, with areas denuded of cartilage included as having zero thickness [39]
- Bone marrow lesion volume (mm^3) by anatomical region: medial and lateral femorotibial region of femur, medial and lateral patellofemoral region of femur, medial and lateral tibia, and patella
- Bone area (mm^2) for anatomical regions: lateral and medial femur (patellofemoral); lateral and medial femur (femorotibial); lateral and medial patella, lateral and medial tibial condyle
- Bone shape by distance along an OA shape vector for femur, tibia and patella
- Index bone area/cartilage thickness.

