#### 9.5.2.4 Statistical Methodology for Secondary Endpoints

For Study Population B, the safety and tolerability of 200 mg MIV-711 for 26 weeks will be studied in OA patients with clinical worsening during the placebo treatment in the MIV-711-201 study. Safety and tolerability will be assessed descriptively in summary tables presented over time.

All other secondary analyses will be undertaken using Study Population A, while they will be undertaken as exploratory analyses on Study Population B.

For Study Population A all secondary outcome variables will be analysed using descriptive summary tables presenting statistics for, number of non-missing values means, medians, standard deviations, minimum and maximum values. Frequency tables (counts and

percentages) will be presented in tables where appropriate. Figures of secondary response over time will be presented as appropriate.

For all outcome variables analysed using a linear model, distributional assumptions will be checked using examination of empirical distributions and model residuals. If necessary, data will be transformed prior to analysis if this improves the model fit, or normalises the distribution of the residuals. Non-parametric methods may be applied if appropriate.

For the analysis of secondary endpoints, alternate statistical methods maybe considered that will include the use of generalised linear models that account for the response variable having a “non-normal” distribution. Additional details will be provided in the SAP.

All secondary outcomes will be summarised descriptively (mean, SD, median, minimum and maximum for continuous data and counts and percentages for categorical data).

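### Group summaries of quantitative bone area and cartilage thickness are confined to medial regions; the other regional measures and bone shape named in Protocol 7.2 are only listed by patient

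*SAP*

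**What the plan says.** Protocol 3.2 states the bone objective at the level of the joint: "To assess the effect of MIV-711 on MRI knee joint bone area". Protocol 7.2, headed as secondary endpoints for Study Population A, then defines the shape-modelling measures by region:

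- bone area: "lateral and medial femur (patellofemoral); lateral and medial femur (femorotibial); lateral and medial patella, lateral and medial tibial condyle"
- cartilage: "Mean cartilage thickness (mm) for each of the anterior, posterior and central regions"
- BML volume: "medial and lateral femorotibial region of femur, medial and lateral patellofemoral region of femur, medial and lateral tibia, and patella"
- shape: "Bone shape by distance along an OA shape vector for femur, tibia and patella"

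It also names an index of bone area and cartilage thickness. SAP 4.5.1 repeats these definitions.

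On reporting, Protocol 9.5.2.4 says: "For Study Population A all secondary outcome variables will be analysed using descriptive summary tables".

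SAP 8.1 limits the descriptive summary to four vendor variables. For bone area the only one is "MRI of the bone area of the medial femur for the target knee" (MF_TAB). The others are CM_FEMUR_THCTAB, CM_TIBIA_THCTAB and TOTAL_BML_VOLUME. SAP 8.1.1 fits the mixed model to the same four, and Tables and Figures 14.2.1.1 to 14.2.1.9 cover nothing else. The remaining variables are in by-patient listings titled as other imaging variables.

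**The concern.** The protocol's measures span the knee, but the SAP reports group-level bone area and cartilage thickness from medial regions alone. Neither document says that the target knee must have mainly medial disease; the knee is chosen on pain and Kellgren-Lawrence grade. Where the disease is mainly lateral or patellofemoral, the tabulated bone area and cartilage thickness describe a different part of the joint.

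This matters more than an ordinary omission of secondary tables. Protocol 2.3 gives the cartilage analysis as one reason for following patients over 52 weeks. The study is descriptive, so the summary tables are its main product on structure. As planned, quantitative bone or cartilage change outside the tabulated regions could be seen at group level only if a reader calculated it from the listings.

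**Working it through.** No power or sample-size figure is involved. The check sets the protocol definitions beside the SAP's table, figure and listing plans and the shells.

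| Measure | Protocol 7.2 | Summary table or model | Listing only |
|---|---|---|---|
| Bone area | medial and lateral parts of femur (patellofemoral and femorotibial), patella and tibia | MF | LF, MT, LT, MP, LP (16.2.6.7.1) |
| Cartilage thickness | anterior, posterior, central | central medial femur, central medial tibia | central lateral femur, central lateral tibia, trochlear femur, patella (16.2.6.7.3) |
| BML volume | by region | total | MF, LF, TrF, MT, LT, P (16.2.6.7.6) |
| Bone shape | femur, tibia, patella | none | three shape vectors (16.2.6.7.2) |

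Counts within the vendor's own scheme:

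- Summarised: 1 + 2 + 1 + 0 = 4 variables.
- Listed only: 5 + 4 + 6 + 3 = 18 variables.
- Bone area is summarised for 1 of 6 vendor regions (1 + 5), cartilage thickness for 2 of 6 (2 + 4) and shape for 0 of 3. BML volume is summarised as the total, without the six-way split.

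The index (Listing 16.2.6.7.7) is counted separately, for two reasons. Protocol 7.2 lists it, but the synopsis and Protocol 3.4 and 7.4.1 treat it as exploratory. SAP 4.5.4 also says it arrives already derived as a change from baseline to Visit 5.

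Two further mismatches concern Protocol 7.2 regions with no vendor output so named. None of the six thickness variables is called anterior or posterior. No femoral patellofemoral bone area appears separately, and the SAP does not say whether MF includes it.

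What does reach a table for the rest of the knee:

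- TOTAL_BML_VOLUME is defined in SAP 4.5.1 as the combined volume over all BML regions, so lateral and patellofemoral lesions are in it.
- MOAKS (SAP 4.5.2) scores lateral, patellar, anterior and posterior subregions. Tables 14.2.2.1 to 14.2.2.4 show shifts from baseline to Visit 5 in the number of affected subregions. SAP 8.2 counts a subregion as affected at a score of 1 or more. A newly affected lateral or patellar subregion can therefore raise the count. Its location is lost, and worsening in a subregion already scored 1 or more does not change the count.

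Finally, disclosure: SAP 4.6 says the study report will explain the difference from the protocol on analysis populations. No similar statement covers the MRI regions, and SAP 8.1 gives no reason for its choice.

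**The case against.** The best defence is that the commitment is met at the level at which the endpoints are enumerated. Protocol 9.5.2.2 lists cartilage thickness loss, BML volume, MOAKS and bone area, and each has at least one summary table. Bone shape is not on that list. A SAP may choose representative regions, and this one names its choice in writing. The study is unpowered and uncontrolled, with safety as its primary endpoint, and 18 more variables in an expected 50 to 80 patients add noise. The listings already give change scores for the regional and shape measures.

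Part of this stands. Choosing representatives is legitimate, the claim for bone shape is weaker than for bone area and cartilage, and the mixed model need not be extended. But 9.5.2.2 only names the measures. Protocol 7.2 defines them, by region and under the secondary-endpoint heading, and SAP 4.5.1 repeats that definition. Listings are not the summary tables that 9.5.2.4 promises, and the selection is neither justified nor recorded as a change.

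A reader might go further and infer three things the documents do not support:

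- That lateral and patellofemoral change is nowhere summarised. Total BML volume and the MOAKS tables contradict this.
- That the anterior and posterior thickness regions were not measured. The documents show only what is output.
- That the regions were picked after seeing data, because the SAP is dated 16 January 2018 and Protocol 10.11 planned the study to end in August 2017. The dates alone do not show this.

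**Conclusion.** The concern holds in a limited form. Four vendor variables are summarised and 18 are only listed. For bone area the tables speak to the medial femur, and for cartilage thickness to the central medial femur and tibia. They cannot carry a quantitative conclusion about the joint as a whole. For BML only the regional breakdown is missing. Bone shape has no group summary at all.

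Two stronger sizes are tempting but cannot be supported. One is a fraction of the protocol's own region counts for bone area and BML: the vendor uses six regions for each, and the mapping to Protocol 7.2 is not given. The other is a percentage by which medial averages understate change in the diseased compartment: neither document gives the share of knees with mainly lateral or patellofemoral disease, and the eligibility criteria of MIV-711-201, from which every patient comes, are not among these documents.

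The conclusion rests on reading Protocol 7.2 as the definition of the secondary endpoints to which 9.5.2.4 applies. It does not touch the primary safety objective.

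**What to change.** 1. Add to SAP 8.1 and the table list descriptive tables (n, mean, SD, median, minimum, maximum; observed and change from baseline, by group and visit) for the 18 variables now only in Listings 16.2.6.7.1, 16.2.6.7.2, 16.2.6.7.3 and 16.2.6.7.6. Use the baseline in SAP section 8, which those listings follow. The footnotes of the existing Table 14.2.1.1 to 14.2.1.3 shells give a different baseline for Group B and should not be copied.
2. Keep the mixed model for the four variables now named.
3. Summarise the bone/cartilage index as a score only, labelled exploratory. It is already a change, so a further change from baseline would be meaningless.
4. State in SAP 8.1 that the modelled bone-area and cartilage results refer to the medial compartment, and why those regions were chosen.
5. Under *Changes to planned analysis*, record any Protocol 7.2 region that the Imorphics analysis does not output: anterior and posterior cartilage thickness, and separate femoral patellofemoral bone area.

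The cost is programming for variables already prepared for listings, with no new scans or reading. The downside is a longer set of descriptive, unadjusted outputs in a small study, which should be presented as such.

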8.1.1 Statistical Analysis – Imorphics MRI Assessments

A linear mixed effects model will be used to assess the behaviour of the MRI response over the entire period of the two studies, i.e. from visit 2 in study MIV-711-201 to visit 5 in study MIV-711-202. The model will include fixed factors for study group (A or B), visit, group*visit interaction, baseline analgesic user (Yes/No), and random effect for site and patient.

Patients considered analgesic users at baseline will be identified via concomitant medication analgesic usage. A patient exposed to a prescribed analgesic and ongoing medication at time of the first 200 mg MIV-711 intake (visit 2 study MIV-711-201 for patients in group A and visit 2 study MIV-711-202 for group B) will be considered as a baseline analgesic user.

The dependent variable in the linear mixed model is the observed MRI score. Separate mixed model analyses will be considered for each of the MRI endpoints noted in section 8.1. The following SAS code will be used as default, but a reduced model may be used in case of convergence issues:

```
PROC MIXED data=;  
  CLASS patient visit group baseline_conmed_pain_use;
```

PAREXEL International Statistical Analysis Plan

Medivir
Protocol: MIV-711-202

Final 1.0
16 January 2018

```
MODEL MRI_score = group visit group*visit baseline_conmed_pain_use/ DDFM=KR ;  
RANDOM site;  
REPEATED visit / SUBJECT=patient TYPE=UN;  
LSMEAN group*visit / diff CL ALPHA=0.1 ;  
RUN;
```

In case of convergence issues, a reduced model will be used to achieve convergence. The first two model reductions that will be considered are the following:

1. Simplify the covariance structure by using a compound symmetry covariance structure instead of unstructured.
2. Omit the random effect of site

The mean level and the change from visit 2 in study MIV-711-201 will be estimated for each population*visit combination in the model above together with the corresponding 90% confidence interval. The estimates and confidence intervals will be tabulated and visualized over visits with the two groups in the same table/figure (see example figures and example table below). In this example table and example figures (Figure 1, Figure 2 and Table 1), 'Population A' and 'Population B' refer to Group A and Group B.

PAREXEL International Statistical Analysis Plan

Medivir
Protocol: MIV-711-202

Final 1.0
16 January 2018

Figure 1 Example figure of estimated mean levels

[figure not shown]
[figure not shown]

Figure 2 Example figure of estimated change from visit 2 (MIV-711-201)

PAREXEL International Statistical Analysis Plan

Medivir
Protocol: MIV-711-202

Final 1.0
16 January 2018

Table 1 Example table of statistical analysis corresponding to Figure 1 and Figure 2.

Endpoint	Population	Visit	N	Estimated Mean level		Estimated Change from Visit 2, Study MIV-711-201	
				LS Mean	95% CI	LS Mean Difference from V2 MIV-711-201	
						95% CI	95% CI
MRI of Bone Area Medial femur region	A	V2:201	nn	xx	(xx, xx)		
		V8:201	nn	xx	(xx, xx)	xx	(xx, xx)
		V5:202	nn	xx	(xx, xx)	xx	(xx, xx)
	B	V2:201	nn	xx	(xx, xx)		
V8:201		nn	xx	(xx, xx)	xx	(xx, xx)	
V5:202		nn	xx	(xx, xx)	xx	(xx, xx)	

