The analysis of data from the proposed study will not be based on a formal statistical analysis since the primary endpoint constitutes safety and tolerability. All efficacy parameters measured in Study MIV-711-201 will also be measured in the proposed study. However, the important difference is that any comparisons will be made from baselines within but not between Study Population A and B. In contrast, in Study MIV-711-201, comparisons will be made between treatment groups with a formally powered analysis regarding the primary endpoint.

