##### **Study Population B**

Patients receiving placebo in Study MIV-711-201 and that had experienced a clinical worsening as defined by increased NRS versus Baseline of  $\geq 2$ .

No comparisons between Study Populations A and B will be undertaken.

Major protocol violators and exclusions from the analysis sets will be identified by a panel, including the clinical project manager, study statistician, and other appropriate clinical study team members.

The following criteria will be used to exclude a patient from the analysis set:

- Incorrect diagnosis
- Any of the prohibited interventions/injuries for the target knee
- Missing more than 7 doses of MIV-711

The panel will review these criteria using soft-locked data prior to data analysis.

The safety analysis set (SAF): all patients receiving at least one dose of either MIV-711.

The primary analysis will be based on Study Population A.

The secondary analysis will be based on Study Population B.

All safety analyses will be based upon the SAF.

Demographic and Baseline characteristics will be evaluated for the SAF.

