8.3.1.1 Statistical Analysis of the NRS Pain Data

The statistical analysis of NRS Pain data will be performed using the same statistical analysis as for the Imorphics MRI described in in section 8.1.1. The output of the statistical analysis will be similar (see example figures and table section 8.1.1.) but will be based on the visits when the NRS assessments were conducted.

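### The efficacy models impose one visit covariance on Groups A and B; the entry rule makes that untenable for target-knee NRS and mis-sizes its week-26 change intervals, while for the other endpoints it is an unchecked assumption

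*SAP*

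**What the plan says.** The default code in SAP 8.1.1 classifies by "CLASS patient visit group baseline_conmed_pain_use", models the mean as "MODEL MRI_score = group visit group*visit baseline_conmed_pain_use/ DDFM=KR", and sets the within-patient covariance with "REPEATED visit / SUBJECT=patient TYPE=UN". There is no `GROUP=` option, so one unstructured matrix serves both groups. If the model does not converge, the first reduction is compound symmetry and the second drops the site effect; neither separates the groups. The reported quantities are set out as follows: "The mean level and the change from visit 2 in study MIV-711-201 will be estimated for each population*visit combination", with confidence limits from "LSMEAN group*visit / diff CL ALPHA=0.1".

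The model is carried to other endpoints. SAP 8.3.1.1 states: "The statistical analysis of NRS Pain data will be performed using the same statistical analysis as for the Imorphics MRI". SAP 8.3.3.1, 8.3.7.2 and 8.3.8.1 do the same for WOMAC, e-diary NRS and the two CTX biomarkers.

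Protocol 5.1, Inclusion Criterion 1, defines the groups by the change in average target-knee NRS from Visit 2 to Visit 8 of study 201: an increase of at most 2 on 200 mg (Group A), or of at least 2 on placebo (Group B). Protocol 2.4 says that "any comparisons will be made from baselines within but not between Study Population A and B", and Protocol 9.1.3 adds: "No comparisons between Study Populations A and B will be undertaken". The documents expect 50 to 80 patients in total. They give no A/B split, no SDs, and no statement that the covariances are equal or will be examined.

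**The concern.** A shared covariance gives correct intervals only if the two groups vary alike. Here the groups were selected on the week-26 change of an outcome that the model then analyses, by rules that cut opposite ends of its distribution. Group B keeps only the upper tail of the change, so its spread is small. Group A loses only its upper tail, so its spread stays large. A pooled variance falls between the two: too large for B and too small for A.

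The loss is in reported precision. In unpowered analyses the estimate and its interval are all that the model delivers. The usual reason for sharing a variance, an efficient between-group comparison, does not apply because the protocol allows only within-group comparisons. Pooling still has one benefit, stability in a small group, which is taken up under the objection.

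**Working it through.** **No plan figure to reproduce.** The documents contain no variance, correlation or precision calculation. Every SD, correlation and split below is an assumption.

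**Formula.** The group-by-visit means are saturated. With complete data, and ignoring the shared analgesic coefficient and the site effect, each group's estimated change is its own mean change, with standard error √(s_p²/n_g), where

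s_p² = [(n_A − 1)s_A² + (n_B − 1)s_B²] / (n_A + n_B − 2).

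The reported interval differs from the correct one by about the factor s_p/s_g, apart from degrees of freedom. The factor does not depend on the confidence level. That matters because the code gives 90% limits while the table shells are headed 95%, which is a separate matter.

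**If the covariances are equal.** The factor is 1. Simulated coverage of the nominal 90% interval was 0.90 in both groups at all six splits tried (25/25, 40/10, 40/20, 60/20, 70/10, 40/40). Pooling alone does no harm.

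**One worked case for week-26 NRS change.** Assume an underlying change with mean −1 and SD 2, rounded to whole points. After the entry rule the SDs are 1.84 in A and 0.80 in B. With 40 and 10 patients:

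- s_p² = (39 × 3.386 + 9 × 0.640)/48 = (132.04 + 5.76)/48 = 2.871, so s_p = 1.694.
- B: 1.694/0.80 = 2.12, so the interval is about twice the correct width.
- A: 1.694/1.84 = 0.92, so it is about 8% too narrow.
- Simulated coverage of the nominal 90% interval: 0.867 in A and 0.998 in B.

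**Range.** Assume whole-number NRS from 0 to 10, baseline at least 4 with mean 6, SD 1.6 to 2.0, between-visit correlation 0.3 to 0.5, mean change 0 to −1.5, n_A 40 to 50 and n_B 8 to 30.

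| Change from Visit 2 of 201 | Group B interval | Group A interval |
|---|---|---|
| Week 26 (Visit 8 of 201) | about 1.7 to 3.3 times too wide | about 5 to 20% too narrow |
| Week 52 (Visit 5 of 202) | about 5 to 13% too wide | about 1 to 5% too narrow |

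**Sensitivity of the lower end.** A simpler model of the change alone, with mean −1.5 to 0 and SD 1.5 to 2.5, gives a B/A SD ratio r of 0.30 to 0.62. Holding the split at 40/10, B's factor is √[(39 + 9r²)/48]/r. For r = 0.30 this is 0.911/0.30 = 3.04; for r = 0.62 it is 0.941/0.62 = 1.52. A wider spread of change therefore lowers the bottom of B's range to about 1.5. In six cases from this model that were run for coverage, the nominal 90% interval covered 0.80 to 0.88 in A and 0.99 to 1.00 in B.

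**Why week 52 is milder.** Selection acts on the Visit 8 change and reaches later visits only through correlation. In the worked case, with correlation 0.5 between the two changes, the week-52 SDs are 1.96 and 1.78. Then s_p² = (39 × 3.842 + 9 × 3.168)/48 = 3.715 and s_p = 1.928, giving factors of 1.08 in B and 0.98 in A.

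**Other endpoints.** The direction depends on an SD ratio that the documents do not give. Over the six splits, a B/A ratio of 0.75 gives coverage of 0.86 to 0.89 in A and 0.95 to 0.97 in B. A ratio of 1.5 gives 0.92 to 0.96 in A and 0.76 to 0.84 in B.

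**The case against.** **Not every interval is wrong.** A reader might infer that the intervals in every model table and figure are wrong. The documents do not support that. Means are separate by group, the intervals hold if the covariances are equal, and no variances are given. Section 8.1.1 is itself the MRI section, and selection was not on MRI.

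**The worst-affected interval is not a drug effect.** B's week-26 change is its entry criterion, so its size is preset by selection. B's response to the drug can only appear after Visit 8, and its week-52 interval errs on the wide side. This largely stands. But the SAP prints the week-26 intervals for both groups, and A's error is towards too narrow.

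**CTX.** If SD scales with the mean and the drug lowers CTX by 30 to 55%, B's raw-scale week-26 level interval would have 0.55 to 0.80 of its correct width. That rests on raw-scale analysis. Protocol 9.5.2.4 provides for residual checks and transformation in linear models, and a log transform would largely remove this difference. The SAP does not repeat the provision, so the concern remains plausible but not established.

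**Estimability.** An unstructured matrix needs 6 × 7/2 = 21 parameters for the six NRS visits and 7 × 8/2 = 28 for the seven CTX visits. A small Group B may not support that, and pooling does stabilise it. This stands, and the fix has to allow for it.

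**The barred comparison.** A reader might also infer that the `diff` option breaches the protocol. It would print A-versus-B lines, but it also yields the within-group contrasts, and no table shell reports an A-minus-B estimate.

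**Missing data.** It would go too far to say that B's missing values are predicted from A's correlations. A pooled matrix uses both groups, NRS at Visits 2 and 8 is needed for entry, and lack of a Visit 8 MRI is an exclusion criterion.

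**Stakes.** The study is unpowered, its primary outcome is descriptive safety, and SAP section 6 also tabulates group-specific SDs, so unpooled precision can be seen.

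**Conclusion.** The point holds in a limited form. SAP 8.1.1 and the analyses that reuse it assume a common covariance without justification or check. For average target-knee NRS the entry rule makes that untenable, and the week-26 change intervals are mis-sized as planned: about 1.7 to 3.3 times too wide in B and about 5 to 20% too narrow in A, under the assumed inputs. The week-52 error is small. For WOMAC and e-diary pain, which are likely to correlate with NRS, and for untransformed CTX, unequal covariance is plausible but cannot be sized from the documents. For MRI there is no evidence either way.

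The direction for NRS follows from the design. The size rests on assumed SDs, correlations, mean changes and group sizes. Severity is minor to moderate: these are secondary or exploratory analyses, and what is affected is reported precision.

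**What to change.** Fit the model separately by group (`BY group`), or add `GROUP=group` to the `REPEATED` statement. Where an unstructured matrix cannot be estimated in Group B, name in advance a parsimonious group-specific structure, such as heterogeneous compound symmetry, or use paired-change t intervals. Apply the same rule to the compound-symmetry fallback, which otherwise keeps the common variance and also forces every pair of visits to have the same change variance. Output only the within-group visit contrasts. If a common covariance is kept for MRI, say why and check it.

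The cost is a line of code, a few sentences in the SAP, and fewer degrees of freedom for Group B. No comparison that the protocol allows is lost. In the simulated NRS cases, separate variances brought nominal 90% coverage to 0.89 to 0.91 in A. In B it was 0.90 to 0.91 at week 52 and 0.87 to 0.90 at week 26, where a small, truncated sample remains a limit.
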